As mentioned previously, the mixed methods design of this pilot RCT reflects our desire to capture the complex independent and interdependent explanatory pathways of the intervention. This is especially crucial during this pilot stage, where we will be paying particular attention to feasibility, context, and unexpected mechanisms that produce change – factors that will influence study outcomes and provide important information regarding scalability and sustainability (Craig et al., 2008; Moore et al., 2015). To fully apprehend these complex explanatory pathways, “represent the best use of the data,” and “provide an adequate assessment of the success or otherwise of an intervention that has effects across a range of domains” (Craig et al., p.3), we have aligned our key outcome variables (Table 1) with the Medical Research Council guidance on evaluating complex interventions and identified more than one primary outcome measure.

Table 1. Key Outcome Variables

Variables	Instruments*
Community integration (psychological and physical)	Community Integration Scale
Social connectedness	
Engulfment	Social Connectedness Scale – Revised Modified Engulfment Scale

Self-esteem	Rosenberg Self-Esteem Scale
Hope	Beck Hopelessness Scale
Psychiatric symptoms	Modified Colorado Symptom Index
Enrollment in education (includes skills training)	Composite checklist
Employment	
Income	Composite checklist
Perceived housing quality	Perceived Housing Quality Scale
Participant perspectives of barriers and facilitators	Individual semi-structured interviews (youth) and focus groups (mentors) Composite checklist (Mentor Evaluation)

*See Table 2 for references and psychometric properties. All will be administered every six months for 30 months (except for the mentor evaluation – see Table 2).

The **primary outcome measures** for this study are: community integration (psychological and physical) and self-esteem. **Secondary outcomes** include: social connectedness, hope, and academic and vocational participation. **Exploratory outcomes** include: engulfment, psychiatric symptoms, income, perceived housing quality, and participant perspectives of intervention barriers and facilitators.

4b. Study Hypothesis

We hypothesize that, for the **primary outcome** measures of community integration and self-esteem:

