1. We will observe better mean scores (community integration and self-esteem) in the participants who receive rent subsidies plus mentorship (intervention group) compared to the participants who receive rent subsidies only (control group) by our **primary endpoint of 18 months** of study participation.

We hypothesise that, for the **secondary outcome** measures of social connectedness, hope, and academic and vocational participation:

1. We will observe better mean scores (social connectedness and hope) in the intervention group relative to participants in the control group by our **secondary endpoint of 18 months** of study participation.
2. Participants in the intervention group will be more likely than the control group to demonstrate sustained engagement in academic and vocational activities (education, employment, and/or skills training) by our **secondary endpoint of 18 months** of study participation.

4c. Quantitative Measures

Quantitative data (Appendix A – Quantitative Data Collection) will be collected at **six points** in time over the course of 30 months: baseline, month six, month 12, month 18, month 24, and month 30. **Nine instruments** (Table 2) will be employed to assess the outcome variables. We have purposely chosen instruments utilized in previous research with young people who have experienced homelessness (e.g., Kidd et al., 2016; Kozloff et al., 2016; McCay et al., 2015) so that meaningful comparisons can be made across studies (Moore et al., 2015) in this nascent area of research. One instrument we do not believe has been used with this population is the Modified Engulfment Scale (McCay & Seeman, 1998). We have included engulfment as an exploratory outcome given the emerging qualitative evidence on the crucial role of identity (self-concept) in a young person's transition away from homelessness (Brueckner et al., 2011; Karabanow et al., 2016; Thulien et al., 2018).

Table 2. Quantitative Instruments

Instrument	Psychometric Information
Beck Hopelessness Scale (Beck, Weissman, Lester, & Trexler, 1974).	This 20-item scale measures motivation, expectations, and feelings about the future (internal consistency $\alpha = .93$).

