Community Integration Scale (Stergiopoulos et al., 2014).	This 11-item scale measures behavioral (e.g., participation in activities) and psychological (e.g., sense of belonging) aspects of community integration. This scale was used extensively in the Chez Soi/At Home study, but psychometric properties have yet to be reported.
Education, Employment, and Income Questionnaire	This 13-item questionnaire assesses education, employment, and income. We developed this questionnaire for the study.
Mentor Evaluation Questionnaire	This 10-item questionnaire assesses mentor effectiveness. It will be completed at month 24 by those in the intervention group. We developed this questionnaire for the study in collaboration with our community partners.
Modified Colorado Symptom Index (Ciarolo et al., 1981).	This 14-item scale measures the presence and frequency of psychiatric symptoms experienced in the past month. (internal consistency $\alpha = .90 - .92$).
Modified Engulfment Scale (McCay & Seeman, 1998).	This 30-item scale measures the degree to which an individual's self-concept is defined by their experience of homelessness (internal consistency $\alpha = .91$). We have adapted the scale for this

	study, substituting “experience of homelessness” for “illness”.
Perceived Housing Quality (Toro et al., 1997).	This seven-item scale measures participant perception of housing choice and quality. This scale was used extensively in the Chez Soi/At Home study, but psychometric properties have yet to be reported. We have shortened it from 10 items (Chez Soi/At Home) to seven relevant items.
Rosenberg Self-Esteem Scale (Rosenberg, 1965).	This 10-item scale measures global self-worth (internal consistency $\alpha = .77 - .88$).
Social Connectedness Scale – Revised (Lee & Robbins, 1995).	This 20-item scale measures belongingness – the degree to which an individual feels connected to others (internal consistency $\alpha = .92$).

4d. Qualitative Measures

Qualitative measures (see Appendix B – Qualitative Data Generation) are an important feature of this study and will consist of: **1) semi-structured individual interviews** (study participants) and **2) focus groups** (mentors).

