One major critique of mixed methods RCTs is that, typically, there is no true integration (i.e., ‘mixing’) of quantitative and qualitative findings at the level of analysis or interpretation (Lewin, Glenton, & Oxman, 2009). Moreover, it is often unclear whether or how the quantitative and qualitative researchers have worked together to maximize the potential synergies between these different approaches (Lewin et al.). With this in mind, our study team, consisting of researchers with quantitative and qualitative expertise, worked together to develop this study protocol and anticipate meeting quarterly to discuss the emerging analysis and to explore (and follow up on) similarities or discrepancies between the quantitative and qualitative data.

5a. Quantitative Data

All analyses will be performed using the intention-to-treat principle; that is, all participants will be included and analyzed in the groups they were originally randomized. Baseline characteristics of the intervention and control groups will be summarized using descriptive statistics (i.e., mean, standard deviation, median and interquartile range for continuous variables, and frequencies and proportions for categorical variables). We will also calculate descriptive statistics for outcomes at each study time point, and will explore differences in trajectories from baseline to 30 months follow-up between intervention and control groups using scatterplots and box-plots. Differences with 95% confidence intervals in continuous outcomes at 18 months (psychological community integration, self-esteem, social connectedness, hope, perceived housing quality, psychiatric symptoms, and sense of engulfment) between participants who received rent subsidies plus mentorship and participants who only received rent subsidies will be estimated using Analysis of Covariance (i.e., linear regression models), including an indicator of intervention group and the baseline value of the outcome. We will perform regression diagnostics and will repeat analyses using the non-parametric Wilcoxon

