rank-sum test if there are extreme outliers or influential observations. Groups will be compared with respect to count outcomes at 18 months (physical community integration) using graphical tools and the non-parametric Wilcoxon rank-sum test. For binary outcomes at 18 months (sustained academic and vocational participation, and income above low income cut-off⁴), differences in proportions with 95% confidence intervals will be estimated and tested using the chi-square or Fisher's exact test. Given the small sample size of this pilot randomized trial, all results will be interpreted with caution and with the intention of generating data and hypotheses for conducting a larger trial.

All efforts will be made to reduce participants' attrition and drop-out. As mentioned previously, we believe our strong relationship with the outreach workers and community agencies will help minimize loss to follow-up (Slesnick et al., 2009). In addition, we have made it very clear in the participant information and consent form that participants in the rent subsidies plus mentorship arm may continue in the study (receiving only rent subsidies) if they are unable to continue in a mentor-mentee relationship.

5b. Qualitative Data

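### Physical community integration, part of a primary outcome, is the only outcome type in section 5a with no planned between-group estimate or 95% confidence interval

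*Combined protocol and SAP*

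**What the plan says.** Section 4a states that the primary outcome measures "for this study are: community integration (psychological and physical) and self-esteem". Section 4b puts both under one hypothesis at the 18-month primary endpoint: "We will observe better mean scores (community integration and self-esteem) in the participants who receive rent subsidies plus mentorship". Table 2 says of the Community Integration Scale: "This 11-item scale measures behavioral (e.g., participation in activities) and psychological (e.g., sense of belonging) aspects of community integration". Section 4c schedules collection "over the course of 30 months: baseline, month six, month 12, month 18, month 24, and month 30", so a baseline value of the physical component will exist.

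Section 5a then plans the 18-month comparisons by outcome type.

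- **Continuous:** "Differences with 95% confidence intervals in continuous outcomes at 18 months (psychological community integration, self-esteem" and five further scales, estimated by analysis of covariance "including an indicator of intervention group and the baseline value of the outcome". A Wilcoxon repeat is added if there are extreme outliers or influential observations.
- **Count:** the groups are compared on "count outcomes at 18 months (physical community integration) using graphical tools and the non-parametric Wilcoxon rank-sum test". Nothing else is specified for this type.
- **Binary** (sustained academic and vocational participation; income above the low income cut-off): a difference in proportions with a 95% CI, plus a chi-square or Fisher's exact test.

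Section 5a also plans summaries for every outcome: "We will also calculate descriptive statistics for outcomes at each study time point". It adds scatterplots and box-plots of trajectories by arm. It says that the results are to be read cautiously and used to generate data and hypotheses for a larger trial.

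**The concern.** Followed as written, the plan gives a p-value and a plot for one component of a primary outcome. Exploratory outcomes such as housing quality, engulfment and income all get an estimate with an interval. The two components of one 11-item scale would be reported in different forms: a baseline-adjusted difference with a CI for one, a rank test for the other.

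Two things are at stake. First, the hypothesis is about mean scores, and a rank-sum test does not estimate a difference in means. Second, whoever designs the larger trial needs the size of the difference and its uncertainty. A test result from 24 participants supplies neither.

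**Working it through.** **Step 1: the text.** The plan gives no power, SD or effect size for this outcome, so there is no figure to reproduce. The check is a comparison within section 5a.

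| Outcome type | Outcomes | Estimate named | 95% CI named | Baseline in the comparison |
|---|---|---|---|---|
| Continuous | 7 | Difference | Yes | Yes |
| Binary | 2 | Difference in proportions | Yes | No |
| Count | 1 (physical community integration) | None | None | No |

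Two of the three types have an estimate and CI. The exception is the one that belongs wholly to a primary outcome. No other section supplies the missing result.

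**Step 2: is an interval feasible at this size?** Yes. Site totals are 12 + 6 + 6 = 24, or 12 per arm. The model already used for the psychological component carries over:

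Y18 = b0 + b1 × arm + b2 × Y0, with CI = b1 ± t(0.975, n − 3) × SE(b1).

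Without the baseline term the width is about 2 × t(0.975, 22) × √(1/12 + 1/12) = 2 × 2.074 × 0.408 = 1.69 SD.

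**Step 3: what would baseline adjustment do?** The documents give neither the count's range nor its SD, nor how the 11 items divide. Assumptions: range 0–7, baseline mean 2.8 (SD 1.77), 12 per arm, latent baseline-to-18-month correlation r. Counts are a bivariate normal thresholded to a beta-binomial shape, with 20,000 simulated trials per row. Mean CI widths are in counts.

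| Scenario | Unadjusted | r = 0 | r = 0.3 | r = 0.5 | r = 0.7 |
|---|---|---|---|---|---|
| Mid-range (control mean 2.8, effect 0.8 SD) | 2.97 | 3.05 (+3%) | 2.92 (−2%) | 2.68 (−10%) | 2.26 (−24%) |
| Floor (means 0.5 v 1.3; 70% v 37% zeros) | 1.97 | 2.02 (+3%) | 1.96 (−1%) | 1.84 (−7%) | 1.62 (−18%) |

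The mid-range unadjusted width is 2.97 / 1.77 = 1.68 SD, which agrees with step 2.

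**Step 4: does the interval hold its coverage?** Ranges are over the four values of r.

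| Scenario | Normal-theory CI | HC3 CI | HC3 width relative to normal-theory |
|---|---|---|---|
| Mid-range, 12 v 12 | about 95% | about 96% | about 7% wider |
| Floor, 12 v 12 | about 95% | about 96% | 7–8% wider |
| Floor, 12 control v 8 intervention | 92–93% | about 95% | about 18% wider |
| Floor, 8 control v 12 intervention | about 96% | about 97% | 1–4% wider |

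Coverage falls short only when a floor is combined with losses concentrated in the intervention arm, and HC3 standard errors restore it.

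**The case against.** **The rank test was chosen deliberately for a small, possibly skewed count.** A reader might infer that the Wilcoxon test is wrong here. It is not: the test is valid and should stay. The gap is in estimation.

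**Summaries are already planned.** If they include mean, SD and n by arm, an unadjusted difference and CI can be worked out. This stands as mitigation. But the plan does not name that difference as a result, and it would leave the baseline count unused.

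**Lack of adjustment is not peculiar to this outcome.** Correct: the binary comparisons are unadjusted too, and the baseline count does appear in the descriptive summaries and trajectory plots. It would overstate the case to say that the plan ignores baseline, or that adjustment must sharpen the result. At r up to 0.3 the change runs from 3% wider to 2% narrower.

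**Other estimates would also close the gap.** A rate ratio, or a mean difference with a bootstrap or permutation CI, would serve. So would a Hodges-Lehmann shift, the natural partner of the Wilcoxon test: with 12 v 12 and no ties, its CI runs from the 38th to the 107th of the 144 ordered differences (95.5% coverage). Near a floor it is uninformative, however. In the floor scenario it is exactly 0 in 43–44% of simulated trials although the true mean difference is 0.8 counts. With no effect, about 27% of its intervals have zero width. The regression is preferred because it answers a hypothesis about means and matches the psychological component, not because it is the only acceptable choice.

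**The floor is conjecture.** Physical integration means activities such as going to a film or community event. Counting back from the stated end dates (24 months of mentoring to September 2021; 30 months of follow-up to March 2022) puts month 18 near March 2021, during the pandemic. But no enrolment dates or count distributions are given. The documents do not show that counts were near zero.

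**Conclusion.** The point holds. Physical community integration is part of a primary outcome, and it is the only outcome type in section 5a without a planned between-group estimate or 95% CI. That conclusion rests on the text alone.

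It is a reporting gap that should be closed. No data are lost and the planned test is not invalid. The documents do not support a reading that the primary analysis is unsound, or that nothing about the size of the difference could be recovered.

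The precision figures are illustrative. They depend on the assumed count range, SD and correlation, and the floor rows depend also on an inferred scenario. Within those assumptions, adjustment changes CI width by +3% to −24% mid-range and +3% to −18% at a floor.

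**What to change.** Keep the graphs, and keep the Wilcoxon rank-sum test as the planned hypothesis test. Add to section 5a:

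> The between-group difference in mean physical community integration at 18 months will be estimated with a 95% CI from a linear regression on intervention group and baseline count, as for psychological community integration; this is the reported effect estimate, and the Wilcoxon test remains the test. If retention is uneven or counts are near zero, the CI will also be given with heteroscedasticity-robust (HC3) standard errors.

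Stating the two roles matters because the methods can disagree. In the floor scenario, power is 37–38% for the Wilcoxon test and 34%, 36%, 41% and 51% for the regression at r = 0, 0.3, 0.5 and 0.7. Giving both intervals whatever the data show would avoid having to define uneven retention and near-zero counts.

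If 18-month data have been seen before the text is added, label the estimate post hoc. The inferred dates make that likely enough to check.

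The cost is two sentences and a few lines of code, with no new data and no test removed. The statistical price is one model degree of freedom, a CI about 3% wider if baseline and 18-month counts are uncorrelated, and a wider robust interval where HC3 is used (about 18% with a floor and 12 control v 8 intervention).

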Findings from this longitudinal pilot randomized controlled trial will help address the gap in our knowledge about the impact of financial support and mentorship on meaningful social integration for young people who have experienced homelessness and are living in market rent housing.

2. Study Aim and Objectives

The overarching aim of this mixed methods study is to assess whether and how rent subsidies and mentorship influence social integration outcomes for formerly homeless young people living in market rent housing in three urban settings.

Specifically, the objectives of this study are to:

1. Determine whether rent subsidies plus mentorship results in better social integration outcomes than only receiving rent subsidies with respect to: a) community integration (psychological and physical); and b) self-esteem at our primary endpoint of 18 months.
2. Determine whether rent subsidies plus mentorship results in better social integration outcomes than only receiving rent subsidies with respect to: a) social connectedness; b) hope; and c) sustained academic and vocational participation at our secondary endpoint of 18 months.
3. Explore whether rent subsidies plus mentorship results in better social integration outcomes than only receiving rent subsidies with respect to: a) income; b) perceived housing quality; c) psychiatric symptoms; and d) sense of engulfment at our exploratory endpoint of 18 months.
4. Integrate qualitative data to facilitate a fuller understanding of the quantitative data and deepen our understanding of what the study participants (young people and mentors) found most beneficial about the intervention and how it could be improved.

3. Study Design

This study will employ a convergent mixed methods design (i.e., quantitative and qualitative data are collected concurrently, and the findings combined) embedded within a RCT and a CBPAR framework (Creswell, 2014; Creswell & Plano Clark, 2018). We believe a mixed methods RCT is appropriate given the complex explanatory pathways (i.e., social and behavioral processes that may act independently and interdependently) of this intervention (Lewin, Glenton, & Oxman, 2009). In addition, the qualitative data will provide insights on contextual factors that may impact the external validity of our findings (Goodkind et al., 2017). Most importantly, this design provides a crucial (and underutilized) youth-informed perspective on social integration.

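### Sustained academic and vocational participation is never defined, and the arms are compared on it only as one unadjusted binary value at 18 months

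*Combined protocol and SAP*

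**What the plan says.** The outcome appears in four places in the combined protocol and SAP, with differing wording.

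- Section 2, objective 2: "sustained academic and vocational participation at our secondary endpoint of 18 months".
- Section 4b, second secondary hypothesis: the mentored group will be "more likely than the control group to demonstrate sustained engagement in academic and vocational activities". Education, employment and skills training are joined by and/or, and the engagement is to be shown *by*, not *at*, 18 months.
- Section 4a, list of secondary outcomes: "social connectedness, hope, and academic and vocational participation". The word *sustained* is absent.
- Section 5a: the outcome is binary at 18 months, introduced by "For binary outcomes at 18 months (sustained academic and vocational participation", and "differences in proportions with 95% confidence intervals will be estimated and tested using the chi-square or Fisher's exact test".

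The data come from a study-developed form (Table 2): "This 13-item questionnaire assesses education, employment, and income". The note to Table 1 gives the schedule: "All will be administered every six months for 30 months". Engagement is therefore recorded at baseline and at months 6, 12 and 18. Section 5a summarises outcomes at every visit and plots trajectories by arm, but its only estimate and test for this outcome is the 18-month comparison of proportions. The continuous outcomes are analysed by covariance analysis with the baseline value in the model. No baseline term is planned for the binary ones.

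**The concern.** Whether participation was sustained depends on a path over time, so the analyst needs a rule that turns visits into yes or no. The supplied text has none. Section 5a gives the companion binary outcome, income, a threshold and a footnote; *sustained* has neither.

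Three things are at stake. First, the rule could be chosen after results are known. Section 3f rules out blinding after assignment, and section 5 has the team meeting quarterly over the emerging analysis. Second, if the rule turns out to be status at the month-18 visit, someone who began work the week before is a success, while someone enrolled at months 6 and 12 who has just finished a course is a failure. Third, with 12 per arm, a chance difference in engagement at baseline carries into the comparison to the extent that engagement persists, and nothing in the planned analysis removes it.

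**Working it through.** **No plan figure to reproduce.** The documents give no expected participation rate, effect size, power or dropout for this outcome. Every rate below is an assumption. From the documents come only 12 per arm (sections 3 and 3a) and the visit schedule (sections 4a and 4c).

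**1. How much the definition matters.** Let engagement follow a two-state chain over months 0, 6, 12 and 18, with baseline proportion p0, six-month retention s (engaged stays engaged) and six-month uptake g (not engaged becomes engaged).

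One case by hand, p0 = 0.5, s = 0.7, g = 0.3. The proportion engaged stays at 0.5 × 0.7 + 0.5 × 0.3 = 0.5 at each visit, so:

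- month 18 only: 0.5
- months 12 and 18: 0.5 × 0.7 = 0.35
- months 6, 12 and 18: 0.5 × 0.7² = 0.245
- engaged at 18 but not at 12: 0.5 × 0.3 = 0.15
- engaged at 6 and 12 but not at 18: 0.5 × 0.7 × 0.3 = 0.105

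Full grid, in per cent; the gap is month 18 only minus all three visits:

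| p0 | s | g | Month 18 only | 12 and 18 | 6, 12 and 18 | Gap | At 18, not 12 | At 6 and 12, not 18 |
|---|---|---|---|---|---|---|---|---|
| 0.30 | 0.70 | 0.15 | 32.8 | 22.6 | 15.4 | 17.4 | 10.2 | 6.6 |
| 0.30 | 0.70 | 0.30 | 48.7 | 32.8 | 20.6 | 28.1 | 16.0 | 8.8 |
| 0.30 | 0.85 | 0.15 | 43.1 | 34.2 | 26.0 | 17.1 | 9.0 | 4.6 |
| 0.30 | 0.85 | 0.30 | 60.6 | 47.2 | 33.6 | 27.0 | 13.3 | 5.9 |
| 0.50 | 0.70 | 0.15 | 36.1 | 26.9 | 20.8 | 15.3 | 9.2 | 8.9 |
| 0.50 | 0.70 | 0.30 | 50.0 | 35.0 | 24.5 | 25.5 | 15.0 | 10.5 |
| 0.50 | 0.85 | 0.15 | 50.0 | 42.5 | 36.1 | 13.9 | 7.5 | 6.4 |
| 0.50 | 0.85 | 0.30 | 63.9 | 52.4 | 41.5 | 22.4 | 11.5 | 7.3 |

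The gap runs from 13.9 to 28.1 points, or 12 × 0.139 = 1.7 to 12 × 0.281 = 3.4 participants per arm. New starters or restarters at month 18 are 7.5 to 16.0% (12 × 0.075 = 0.9 to 12 × 0.16 = 1.9 per arm). Those engaged at months 6 and 12 but not 18 are 4.6 to 10.5% (0.6 to 1.3 per arm).

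**2. Baseline imbalance.** If half are engaged at baseline, the chance that the arms differ by at least 4 of 12 is 2 × P(Bin(24, 0.5) ≤ 8) = 2 × 0.0758 = 0.152.

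**3. Precision of the planned test.** Exact power of Fisher's test, 12 v 12, two-sided 0.05 (the level is inferred from the 95% intervals): 0.21 for 40% v 70%, 0.39 for 30% v 70%, 0.61 for 20% v 70%.

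**4. Gain from the visit count.** The same chain was simulated at 12 per arm with no missed visits. Fisher's test on month-18 status was compared with a linear model for visits engaged (0 to 3) containing arm and baseline engagement (20,000 trials per setting).

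- Equal rates in both arms: the linear model rejected in 4.9 to 5.3% of trials and Fisher's test in 1.8 to 2.5%.
- Control s = 0.70, g = 0.15 against mentored s = 0.85, g = 0.30, with p0 = 0.3 or 0.5: power 0.18 for Fisher, 0.30 for the count model.
- Other assumed rate sets gave gains from 0.23 to 0.38, 0.31 to 0.52 and 0.39 to 0.63.

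Part of the gain reflects the conservatism of Fisher's test at this size; the rest comes from using three visits and the baseline.

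**The case against.** The strongest reply is that section 5a does not say month-18 status alone. A binary variable evaluated at 18 months can be built from the visits up to then, and the hypothesis, "demonstrate sustained engagement in academic and vocational activities (education, employment, and/or skills training) by our" the 18-month endpoint, fits that reading. The questionnaire items are in Appendix A, which is not in the supplied text. Start dates, a look-back period or a completion item may be there, and could separate a one-week starter from a long-term participant. This stands. A reader might infer that the plan uses a snapshot and therefore misclassifies starters and completers. The snapshot reading has some support, since *at 18 months* means the visit value for the continuous scales in the same section, but the documents do not settle it.

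Second, the earlier visits are not ignored: section 5a describes outcomes at each time point and explores trajectories by arm. That also stands, though no estimate or test of this outcome is attached to it.

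Third, any particular cut-off, such as engagement at both months 12 and 18, is a preference and would itself be two snapshots. Agreed; what is missing is a stated rule, not one specific rule.

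Fourth, this is a secondary outcome in a 24-person pilot whose results are to be read cautiously and used to plan a larger trial. That limits the severity. It does not remove the point, because a larger trial cannot plan from an event rate whose definition is unknown.

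**Conclusion.** The point holds in this form: *sustained* has no operational definition in the supplied text, the wording differs between sections 2, 4a, 4b and 5a, and the only planned between-arm estimate and test is an unadjusted comparison of one binary value. Misclassification of late starters and recent completers is conditional on scoring month-18 status alone.

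On size, the choice between a month-18 and an all-three-visit definition moves the proportion by about 14 to 28 points, or 2 to 3 participants per arm, under assumed baseline engagement of 0.3 to 0.5, retention of 0.70 to 0.85 and uptake of 0.15 to 0.30. A reader might infer a wider spread, for example from 60% down to 0.6³ = 22%, a gap of 38 points. That needs engagement at successive six-month visits to be independent, which is implausible; perfect persistence would give no gap at all. No figure in the documents is shown to be wrong.

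The visit count with baseline adjustment is worth adding whichever way the binary outcome is defined. It measures persistence directly, uses data already collected, and in simulation kept type I error near 5% with higher power than the month-18 Fisher test. Importance is moderate.

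**What to change.** In section 5a:

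1. Keep the binary outcome. Before any further comparison by arm, state its derivation from the visits up to month 18: which visits or duration count, which activities qualify, and how completers, late starters and missed visits are scored. Check that the questionnaire records what the rule needs, programme completion in particular.
2. Add the number of visits engaged in education, employment or skills training (0 to 3 over months 6, 12 and 18). Compare the arms by a difference in means with 95% CI from a linear model with baseline engagement (yes/no) as covariate.
3. Use one name for the outcome in sections 2, 4a, 4b and 5a.

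The cost is wording, one extra analysis, and a missed-visit rule, which matters more once several visits are used. No new data collection is needed for the count if the form records current engagement at each visit.

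Timing needs honesty. Section 3ai already describes mentoring meetings up to the September 2021 end of the intervention in the past tense. If that date is month 24, month 18 fell around March 2021 or earlier, so those data may already be in hand. If they have been seen by arm, label the addition post hoc and say when the binary rule was fixed.
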